### **Treatment-emergent Adverse Event (TEAE)**

Treatment-emergent adverse events are defined as events with onset dates occurring on treatment or events that worsen on treatment.

### **Abnormal Laboratory Findings and Other Abnormal Investigational Findings**

Abnormal laboratory findings and other abnormal investigational findings (eg, on an ECG tracing) should not be reported as AEs unless they are associated with clinical signs and symptoms, lead to treatment discontinuation, or are considered otherwise medically important by the Investigator. If a laboratory abnormality fulfills these criteria, the identified medical condition (eg, anemia, increased ALT) must be reported as the AE rather than the abnormal value itself.

### **Adverse Drug Reaction (ADR)**

Adverse drug reactions are defined in this study as any AEs suspected to be related to study treatment by the Investigator and/or Sponsor.

### **Serious Adverse Event**

An SAE is any untoward medical occurrence that at any dose:

- Results in death.
- Is life-threatening. (Note: The term “life-threatening” refers to an event in which the subject is at risk of death at the time of the event, not an event that hypothetically might have caused death if it was more severe.)
- Requires inpatient hospitalization or prolongs an existing hospitalization.
- Results in persistent or significant disability or incapacity.
- Is a congenital anomaly or birth defect.
- Is otherwise considered to be medically important.

Note: important medical events that may not result in death, be life threatening, or require hospitalization may be considered as SAEs when, based upon appropriate medical judgment, they

may jeopardize the subject or may require medical or surgical intervention to prevent one of the outcomes listed above. Examples of such events include allergic bronchospasm requiring intensive treatment in an emergency department or at home, blood dyscrasias or convulsions that do not result in inpatient hospitalization, or the development of drug dependency or drug abuse.

For the purposes of reporting, any suspected transmission of an infectious agent via an IMP is also considered an SAE, as described in Section 7.4.1.4.

#### **Events that Do Not Meet the Definition of an SAE**

Elective hospitalizations to administer, or to simplify trial treatment or trial procedures (eg, an overnight stay to facilitate therapy and related hydration therapy application) are not considered SAEs. However, all events leading to unplanned hospitalizations or unplanned prolongation of an elective hospitalization (eg, undesirable effects of any administered treatment) must be documented and reported as SAEs.

#### **Events Not to Be Considered as AEs/SAEs**

Medical conditions present at the initial trial visit that do not worsen in severity or frequency during the trial are defined as Baseline Medical Conditions, and are not to be considered AEs.

#### **AE/SAEs Observed in Association with Disease Progression**

Progression of the disease/disorder being studied, assessed by measurement of lesions on radiographs or other methods as well as associated clinical signs or symptoms (including laboratory abnormalities), should not be reported as an (S)AE, unless the subject's general condition is more severe than expected for the participant's condition and/or unless the outcome is fatal within the AE reporting period (as defined in Section 7.4.1.3).

#### **Predefined AEs of Special Interest for Safety Monitoring**

Any AE that is suspected to be a potential irAE, as well as IRRs, will be considered an adverse event of special interest.

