Avelumab is characterized by 2 main recognized types of adverse events: irAEs and IRRs (refer to IB, Section 5.3.1.3.1.6 and Section 5.3.1.3.1.7). Because inhibition of PD-L1 stimulates the immune system, inflammatory reactions collectively referred to as irAEs might occur (Weber 2015; Postow 2015; Naidoo 2015). Immune-related AEs are a known class effect of ICIs and may include pneumonitis, colitis, hepatitis, endocrinopathies, dermatitis, nephritis and renal dysfunction, encephalitis, eye disorders (including uveitis and iritis), and other immune-mediated reactions (including myositis and myocarditis). The majority of irAEs have been mild and respond to immunosuppressive treatment (ie, glucocorticoids). Guidance is provided to Investigators that any AE suspected to have an underlying immune-mediated mechanism, and without other confirmed etiology, should be considered immune related and managed according to guidelines described in the protocol.

In addition to irAEs, the other recognized toxicity of avelumab is IRRs (refer to the IB for additional information). Infusion-related reactions frequently occur with other monoclonal antibodies commonly used in children, including rituximab and infliximab. Studies suggest that the rate of infusion reactions is similar in adults and in children, including children  $\leq 5$  years old (Dale 2014; Aeschlimann 2014).

Little is known about the long-term effects of checkpoint inhibition on the developing immune system, although preclinical data suggest a role for PD-L1 in the development and function of T cells (Francisco 2009). Reassuringly, there were no changes in absolute lymphocyte count and in frequency of immune-cell subsets in peripheral blood mononuclear cells obtained from adult cancer subjects pre- and post-treatment with avelumab (Lepone 2015). Given the expected poor survival of the subject population to be enrolled on this trial, the potential benefit of therapeutic effect outweighs the theoretical risk of long-term immune dysfunction.

In summary, based on the wide therapeutic index and the lack of specific safety concerns in the pediatric age group, the starting dose in the dose-finding part of the study was selected to be the adult RP2D, 10 mg/kg every 2 weeks. Detailed guidelines on the early recognition and management of irAEs and IRRs will be provided to the Investigators, subjects, and caregivers.

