#### 6.5.5.3 Immune-related Adverse Events

Because inhibition of PD-L1 stimulates the immune system, irAEs may occur. Treatment of irAEs is mainly dependent upon severity (NCI-CTCAE grade):

- Grade 1 to 2: treat symptomatically or with moderate-dose steroids, more frequent monitoring
- Grade 1 to 2 (persistent): manage similar to high-grade AE (Grade 3 to 4)
- Grade 3 to 4: treat with high-dose corticosteroids.

Treatment of irAEs should follow guidelines set forth in [Table 5](#).

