**Table 5 Management of Immune-related Adverse Events**

Gastrointestinal irAEs		
Severity of Diarrhea/Colitis (NCI-CTCAE v4.03)	Management	Follow-up
Grade 1 Diarrhea: < 4 stools/day over Baseline Colitis: asymptomatic	Continue avelumab therapy Symptomatic treatment, eg, loperamide)	Close monitoring for worsening symptoms Educate subject to report worsening immediately If worsens: Treat as Grade 2, 3, or 4
Grade 2 Diarrhea: 4 to 6 stools per day over Baseline; iv fluids indicated < 24 hours; not interfering with ADL Colitis: abdominal pain; blood in stool	Delay avelumab therapy Symptomatic treatment	If improves to Grade 1: Resume avelumab therapy  If persists > 5 to 7 days or recurs: Treat as Grade 3 to 4
Grade 3 to 4 Diarrhea (Grade 3): ≥ 7 stools per day over Baseline; incontinence; iv fluids ≥ 24 hours; interfering with ADL Colitis (Grade 3): severe abdominal pain, medical intervention indicated, peritoneal signs Grade 4: life-threatening, perforation	Withhold avelumab for Grade 3 Permanently discontinue avelumab for Grade 4 or recurrent Grade 3. 1.0 to 2.0 mg/kg/day prednisone or equivalent Add prophylactic antibiotics for opportunistic infections Consider lower endoscopy	If improves: Continue steroids until Grade 1, then taper over at least 1 month, resume avelumab therapy following steroids taper (for initial Grade 3).  If worsens, persists > 3 to 5 days, or recurs after improvement: Add infliximab 5 mg/kg (if no contraindication), Note: Infliximab should not be used in cases of perforation or sepsis
Dermatological irAEs		
Grade of Rash (NCI-CTCAE v4.03)	Management	Follow-up
Grade 1 to 2 Covering ≤ 30% body surface area	Continue avelumab therapy Symptomatic therapy (eg, antihistamines, topical steroids)	If persists > 1 to 2 weeks or recurs: Withhold avelumab therapy Consider skin biopsy Delay avelumab therapy Consider 0.5 to 1.0 mg/kg/day prednisone or equivalent. Once improving, taper steroids over at least 1 month, consider prophylactic antibiotics for opportunistic infections, and resume avelumab therapy following steroids taper If worsens: Treat as Grade 3 to 4

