Primary Objective	To evaluate the safety and tolerability of avelumab	
Primary Endpoint
 
 Occurrence and severity of treatment-emergent adverse events (TEAEs) \geq Grade 3 according to National Cancer Institute Common Terminology Criteria for Adverse Events (NCI-CTCAE) version 4.03 
Secondary Endpoints
 
 Vital signs (including blood pressure and heart rate) Occurrence and severity of TEAEs, AEs of special interest, and treatment-related AEs, and incidence of laboratory abnormalities as graded by NCI-CTCAE version 4.03 	
 15.2 Adverse Events 15.5 Vital Signs 15.2 Adverse Events
	To determine the recommended Phase II dose (RP2D) of avelumab in pediatric subjects 0 to < 18 years of age with solid tumors and lymphoma	
Primary Endpoint
 
 Dose limiting toxicities (DLTs) to determine RP2D 	15.1 Dose-Limiting Toxicities
Secondary Objective	To assess antitumor activity of avelumab by determining the ORR according to RECIST 1.1 and as adjudicated by the Investigator in pediatric subjects with solid tumors and lymphoma treated with avelumab	
Secondary Endpoint
 
 Confirmed BOR according to RECIST 1.1 and as adjudicated by the Investigator 	14.1 Confirmed Best Overall Response
	To assess progression-free survival (PFS) based on Investigator assessments, duration of response (DOR), time to response (TTR), and overall survival (OS)	
Secondary Endpoint:
 
 DOR, TTR, PFS per RECIST 1.1 and as adjudicated by the Investigator and OS 	
 14.2 Duration of Response 14.3 Time to Response 14.4 Progression Free Survival 14.5 Overall Survival
	To characterize the pharmacokinetics (PK) of avelumab	
Secondary Endpoint:
 
 Single- and multiple-dose PK profiles of avelumab (ie, C_{max}, AUC, $t_{1/2}$, and C_{trough}, as data permit) 	16.1 Pharmacokinetics
	To assess the immunogenicity of avelumab	
Secondary Endpoint:
 
 Immunogenicity as measured by avelumab anti-drug antibodies (ADA), including neutralizing antibodies (nAbs) 	16.2 Immunogenicity

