15.2 Adverse Events (Primary and Secondary Endpoints - Phase I)

Treatment emergent adverse events (TEAEs) are those events with onset dates occurring during the on-treatment period for the first time, or if the worsening of an event is during the on-treatment period as defined in Section 9.

TEAEs of grade ≥ 3 are a primary endpoint for the study. The analysis is described below in section 15.2.1. Secondary endpoints related to adverse events for this study include the following:

- Occurrence and severity of TEAEs (See section 15.2.1 for a description of the analysis.)
- AEs of special interest including immune-related adverse events and infusion related reactions (See section 15.3.3 for a description of the analysis)
- Study drug related adverse events. (See section 15.2.1 for a description of the analysis.)

All analyses described in Section 15.2 and 15.3 will be based on TEAEs if not otherwise specified. The AE listings will include all AEs (whether treatment-emergent or not). AEs outside the on-treatment period will be flagged in the listings.

The following categories of TEAEs are defined for reporting:

- **Related Adverse Events (secondary endpoint):** adverse events with relationship to study drug (as recorded on the AE eCRF page, Relationship with study drug = Related) reported by the investigator and those of unknown relationship (i.e. no answer to the question “Relationship with Avelumab”).
- **Serious Adverse Events (SAE):** serious adverse events (as recorded on the AE eCRF page, Serious Adverse Event = Yes).
- **Adverse Events Leading to Treatment Discontinuation:** adverse events leading to permanent discontinuation of study treatment (as recorded on the AE eCRF page, Action taken with study treatment = Drug withdrawn).
- **Adverse Events Leading to Death:** adverse event leading to death (as recorded on the AE eCRF page, Outcome = Fatal, as well as AEs of Grade 5).
- **TEAEs of Special Interest (secondary endpoint)**
 - **Immune Related Adverse Events (irAE):** For SMC meetings, potential irAEs will be identified according to a pre-specified search list of MedDRA PTs, documented in a version-controlled repository maintained by the Sponsor. For the final analysis, immune related adverse events according to case definition classified by medical review. Details are included in Table 10 in Appendix I.

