Immune-mediated rash, Immune-mediated colitis, Immune-mediated pneumonitis, Immune-mediated hepatitis, Immune-mediated nephritis and renal dysfunction, Immune-mediated endocrinopathies (Thyroid disorders: Hypothyroidism, Hyperthyroidism, and Thyroiditis), Immune-mediated endocrinopathies (Adrenal insufficiency, Immune-mediated endocrinopathies (Type 1 Diabetes Mellitus), Immune-mediated endocrinopathies (Pituitary dysfunction), Immune-mediated endocrinopathies (Hypogonadism), Other immune-mediated adverse events. Further details e.g. MeDDRA PT queries are regularly updated based on the current MeDRA version.

In order to standardize the MedDRA PT queries as much as possible, High Level Terms (HLT) and Standardized MedDRA Queries (SMQ) will be used whenever a choice, that is considered reflective of the events of interest, is available.

Level 2:

In a second level (medical review), the potential immune-mediated AEs identified from the search performed at Level 1, will be reviewed by qualified medical personnel to determine whether the AE meets the criteria (case definition) for an immune-mediated adverse reaction based on the following algorithm:

Table 10 Algorithm for immune-related adverse reactions

Criteria	Description
Onset	AE onset after 1st avelumab administration until up to 90 days after last dose
Duration	AE does not spontaneously resolve (i.e., without corticosteroids/ immunosuppressant treatment) within 7 days after onset
Immunosuppressive therapy	AE treated with corticosteroid or other immunosuppressant therapy. For endocrinopathies only: AE required hormone replacement* and /or (corticosteroid or other immunosuppressive therapy)
Etiology	No other clear etiology or Histopathology/biopsy consistent with immune-mediated event
All criteria listed in the left column need to be fulfilled for an event to meet the case definition of immune-mediated reaction.	
*Hormone replacement will be evaluated for specific endocrinopathy disorders only as follows: 
 • Thyroid disorders (HLT): Thyroid therapy (ATC codes (H03A, H03B)) • Diabetes mellitus (including hyperglycaemia): Insulin (ATC code A10A) 	

Infusion related reactions are identified based on a list of MedDRA PTs and criteria on the timely relationship according to Table 11.

Table 11 Criteria for infusion related reactions

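### The final irAE tables use a narrower, treatment-dependent case definition than the protocol's suspicion-based AE of special interest, and SAP Section 7 does not declare the change

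*Protocol*

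**What the plan says.** Protocol 7.4.1.1 gives the only definition of the term in the protocol: "Any AE that is suspected to be a potential irAE, as well as IRRs, will be considered an adverse event of special interest". It sets no condition on treatment, duration or confirmation. Protocol Section 5.2 (Justification for Dose) points the same way for investigators: "any AE suspected to have an underlying immune-mediated mechanism, and without other confirmed etiology, should be considered immune related".

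The endpoint appears in Protocol 8.3.2 and in SAP Section 5: "Occurrence and severity of TEAEs, AEs of special interest, and treatment-related AEs, and incidence of laboratory abnormalities as graded by NCI-CTCAE version 4.03". SAP 15.2 gives its scope as "AEs of special interest including immune-related adverse events and infusion related reactions".

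SAP 15.2 then splits the irAE part in two. For SMC meetings, potential irAEs come from a list of MedDRA preferred terms. For the report the rule is different: "For the final analysis, immune related adverse events according to case definition classified by medical review". That case definition is Table 10 in SAP Appendix I. It has four criteria, all required: an onset window, no spontaneous resolution within 7 days, treatment, and etiology or histology. The treatment criterion reads "AE treated with corticosteroid or other immunosuppressant therapy". Endocrinopathies have an alternative hormone route, which the footnote spells out for thyroid disorders and diabetes only.

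The irAE tables in SAP 15.3.3 are tables of irAEs in this sense. No table of potential irAEs is planned for the report. SAP Section 7 states that the methods accord with protocol version 2.0 and then lists changes to the PK, immunogenicity and biomarker analysis sets only.

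**The concern.** The protocol asks whether someone suspected an immune cause. The SAP's final analysis asks whether the event was also treated in a particular way and failed to resolve on its own. Treatment is largely set by the protocol's own management table, and that table has irAE rows without steroids. Some events that the protocol itself calls irAEs can therefore never enter the endpoint's tables if they are managed as written and settle.

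Two things are at stake. First, the reported irAE incidence is at or below the incidence under the protocol's definition, and the rows affected are low grade, so the severity distribution may shift upward. Second, the SMC and the study report will rest on different irAE counts. A reader who goes to Section 7 to find departures from the protocol will not learn this.

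**Working it through.** No formula or planned figure applies to the definition, and the documents give no irAE rate to reproduce. The check sets the rows of protocol Table 5 against the treatment criterion of SAP Table 10.

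| Protocol Table 5 row | Management at that step | Can it meet the Table 10 treatment criterion? |
|---|---|---|
| Grade 1 diarrhea/colitis | "Continue avelumab therapy Symptomatic treatment, eg, loperamide" | No, unless it worsens and is then given steroids |
| Grade 2 diarrhea/colitis | Delay, symptomatic treatment | No if it settles; yes if it persists or recurs and moves to the Grade 3 to 4 row, which includes prednisone |
| Grade 1 to 2 rash | Antihistamines or topical steroids as examples | No with antihistamines alone; unclear with topical steroids, since Table 10 names no route |
| Grade 1 pneumonitis, liver, kidney | Monitoring, no steroid | No at that step, but see the next paragraph |
| Thyroid disorders, diabetes | Hormone, anti-thyroid or insulin treatment | Yes, through the listed drug classes, without steroids |

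The fourth row needs a limit. Protocol 7.4.1.1 keeps abnormal laboratory and other investigational findings out of AE reporting unless they come with signs or symptoms, lead to discontinuation, or are judged medically important. Grade 1 liver and creatinine changes, and pneumonitis seen only on imaging, will often not be AEs, so they would not be AEs of special interest under the protocol either. They belong to this point only when they are reported as AEs.

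Protocol 6.5.5.3 shows that the outcome depends on the course of the event: "Grade 1 to 2: treat symptomatically or with moderate-dose steroids, more frequent monitoring". Its next line manages persistent Grade 1 to 2 events like high-grade ones, for which it gives high-dose corticosteroids. A persistent low-grade event can therefore qualify under Table 10, provided the other three criteria are met.

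What is left out is a suspected irAE, reported as an AE, that receives no immunosuppressant (and no listed hormone treatment) at any stage. The 7-day criterion also removes events that resolve on their own within that time.

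The effect of one omitted subject on incidence is 1/n. Phase I plans 12 to 36 subjects:

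- n = 12: 1/12 = 8.3 percentage points
- n = 36: 1/36 = 2.8 percentage points

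An omitted subject here is one whose only suspected irAEs fail Table 10. How many there would be cannot be derived, because the documents give no irAE frequency by grade or by treatment.

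**The case against.** The strongest defense is that the protocol left this to the SAP. The heading over the definition in Protocol 7.4.1.1 refers to safety monitoring, and the SAP does use the broad search for exactly that, in SMC meetings. Protocol 8.5.3.3 speaks of AEs of special interest such as irAEs, not of potential irAEs, and refers to the SAP for further detail. The two levels are set out openly in SAP 15.2 and Appendix I, so the different counts are by design. A strict case definition also has real value for attributing events.

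Much of this stands. The adjudicated definition is legitimate and should stay. It does not, however, make the narrower count equal to the endpoint: the protocol has one definition of the term, and the final tables apply another. Section 7 records small wording changes to analysis sets but not this.

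It is also true that little information disappears. Excluded treatment-emergent events stay in the TEAE tables by SOC, PT and worst grade (SAP 15.2.1). All AEs are listed, and gradable laboratory abnormalities are tabulated separately (SAP 15.4.1). IRRs are counted under Table 11 with no treatment condition. What is lost is the identification and the total of these events as AEs of special interest.

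A reader might infer more: that no Grade 1 gut, liver, kidney or lung event could ever appear in the worst-grade irAE table. The documents do not support that. Events that persist or worsen can receive steroids and qualify, and many Grade 1 laboratory or imaging findings are not AEs in the first place. Nor do they support any particular estimate of how far incidence is understated.

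**Conclusion.** The mismatch is real and undeclared, and its reach is limited. The irAE part of a secondary endpoint will be reported on a narrower definition than the protocol gives. The clearest examples are Grade 1 diarrhea or colitis managed symptomatically, and Grade 2 diarrhea or colitis that settles with delay and symptomatic treatment. The direction is toward fewer reported irAEs; the size is unknown beyond 2.8 to 8.3 points per omitted subject over the planned sample sizes.

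This rests on two assumptions: that such events are suspected and reported as AEs, and that they are managed as Table 5 describes without later immunosuppression. No DLT count, MTD or RP2D rule uses the irAE classification, so dose decisions are not affected. The change is worth making because it is cheap and brings the report closer to its stated endpoint.

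**What to change.** In SAP 15.3.3, add a table of treatment-emergent potential irAEs, taken from the Level 1 preferred-term search in Appendix I, by SOC, PT and worst grade. Label it as search-based and as the summary closest to the protocol's definition. Keep the Table 10 cases as a separate, labelled summary. In SAP Section 7, state that AEs of special interest are reported at two levels and that the adjudicated level is narrower than Protocol 7.4.1.1.

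The cost is one extra table from a search that is already the first step of the planned review. The limitation should be in the label: the search selects by term, not by recorded suspicion. It will include some non-immune events and could miss a suspected event coded outside the list. The change concerns reporting only and alters no clinical management.
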